9.9.3 Exploratory Analyses

Clinician Administered PTSD Scale-4 (CAPS-4)

- The percentage of subjects who achieve a 30% drop in CAPS-4 global score at the primary endpoint (visit 12) will be an indirect measure of clinical significance. Descriptive statistics will be computed and displayed by Stage 1 treatment groups.
- The percentage of subjects who no longer meet PTSD diagnostic criteria according to the CAPS-4 at the primary endpoint (visit 12) will be an indirect measure of clinical significance. Descriptive statistics will be computed and displayed by Stage 1 treatment groups.

- CAPS-4 Subscale Scores (B, C, D, F) at the primary endpoint (visit 12) will be analyzed in the same manner as the primary analysis of the global score. Descriptive statistics will be computed and displayed by Stage 1 treatment groups.
- Active dose 1 (125mg) and Active dose 2 (100mg) CAPS data at the primary endpoint will be tested for equivalence using confidence intervals. If the two groups are found to be equivalent, then outcomes for the active dose groups will be combined and will be tested for significant differences from the comparator group using difference scores in independent sample t-tests, with p value set at 0.05.
- Comparison of the effect of a third experimental session with either Active dose 1 or Active dose 2 may be conducted if sufficient group sizes are attained, and analyses comparing outcomes at third session may be conducted with and without Active dose 2 participants who elected to take Active dose 1 during the third experimental session.
- Two regression analyses will be conducted using (1) all subjects with a Frequency score of 2 or greater and an Intensity score of 2 or greater on the CAPS Associated Features 29 or 30 at baseline and (2) baseline DES-II total score as baseline covariates to determine whether the dissociative subtype of PTSD is predictive of treatment outcomes.
- Here is my suggestion for wording the bullet point above: To determine if baseline variables that assess disassociation are predictive of CAPS Global Severity Score at the Primary Endpoint (dependent variable), a multiple regression analysis will include the following independent variables at baseline (1) dichotomous variable defined as Frequency of 2 or greater and Intensity of 2 or greater on the CAPS Associated Features 29 or the alternative (2) dichotomous variable defined as Frequency of 2 or greater and Intensity of 2 or greater on the CAPS Associated Features 30 or the alternative, and (3) DES-II total score.
-

PTSD Diagnostic Scale (PDS)

A repeated measures analysis of variance (ANOVA) will be performed upon PDS scores at baseline, after experimental sessions (visits 4 and 13) and at the end of Stage 1 (visit 17), with p value set at 0.05. Stage I treatment group will serve as a between-subjects factor. Results of repeated measures ANOVA analysis will be used to examine the effects of each experimental session on self-reported PTSD symptom severity.

Clinician Administered PTSD Scale-4 (CAPS-4) and PTSD Diagnostic Scale (PDS)

PDS and CAPS scores will be correlated via Pearson's product moment correlation at baseline and the timepoint that the primary efficacy is measured to provide a comparison of a self-report measure with a clinician-administered measure of PTSD symptoms.

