12.0 Data Analysis

The Sponsor will judge the clinical and statistical significance of the study based on a comparison of observer-blind data collected at baseline and the primary endpoint using the primary outcome measure, which is the CAPS. Descriptive statistics will be computed overall and within the three dose conditions for all available data from outcome measures, including minimum, maximum, average, and standard deviation. Distributional characteristics will be examined for outliers and extreme values and, if either is evident, nonparametric statistics will be utilized in the analysis. Effect size of the three doses for all outcome measures for Stage 1, Stage 2, and 12 months after the final experimental session will be estimated using Cohen's techniques.

The Sponsor will examine each active dose group and the comparator dose group for homogeneity through comparing demographic characteristics. There is no expectation that conditions will differ in composition by gender, race or ethnicity, duration of PTSD diagnosis or presence versus absence of other permitted psychiatric disorders, as depression. However, owing to small sample size, such variations may arise by chance.

The Sponsor will examine CAPS scores for the primary outcome analysis at baseline and the primary endpoint in each active dose and comparator dose conditions. Active dose 1 and active dose 2 CAPS data at the primary endpoint will be tested for equivalence using confidence intervals. If the two groups are found to be equivalent, then outcomes for the active dose groups will be combined and will be tested for significant differences from the comparator group using difference scores in independent sample t-tests, with p value set at 0.05. If CAPS scores for active dose 1 are not equivalent to active dose 2, then analysis of variance (ANOVA) will be used to compare outcomes from all three groups. Additional exploratory analyses comparing the effect of a third experimental session with either active dose 1 or active dose 2 may be conducted if sufficient group sizes are attained, and analyses comparing outcomes at third session may be conducted with and without active dose 2 participants who elected to take active dose 1 during the third experimental session.

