The sponsor will compare baseline and primary endpoint RBANS and PASAT scores in each active dose group and comparator dose groups. Active dose 1 and active dose 2 RBANS and PASAT data will be tested for equivalence using confidence intervals. If the two groups are found to be equivalent, then outcomes for the active dose groups will be combined and will be tested for significant differences from the comparator group using difference scores in independent sample t-tests, with p value set at 0.05. If scores for active dose 1 are not equivalent to active dose 2, then analysis of variance (ANOVA) will be used to compare outcomes from all three groups. The sponsor will examine the effects of maximal exposure to MDMA on neurocognitive function using the RBANS and PASAT by performing a within-subject repeated measures ANOVA with time of administration as a within-subjects factor.

The sponsor will collect ratings of adherence to the treatment manual from specifically selected types of sessions. Descriptive statistics will be computed for each adherence scale within a given session. The sponsor will explore the factors and structure of the measures of adherence to assist in further development of adherence and competence measures. If sufficient data is available, the sponsor will correlate the mean adherence ratings for adherence scale and session type with Global CAPS scores to investigate the effects of adherence to the treatment manual on reduction in PTSD symptoms. If it is found that there are specific factors within the adherence scales, then the factor will be correlated with Global CAPS score.

Subjects who discontinue treatment prior to the primary endpoint will be asked to complete an outcome assessment prior to continuing to the long-term follow-up. The data from these subjects will be tested for equivalence to data from subjects completing the study per protocol. If found to be equivalent, data from these subjects will be presented as an exploratory Intent-to-treat analysis to examine results without bias towards subjects more likely to complete the study per protocol, with last observation carried forward.

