12.1 Statistical Power

This is a pilot study intended to collect and compare estimates of effect size for each active dose and the comparator dose. The study is underpowered for detection of differences of a small or moderate effect size, and it may detect differences if the effect size is large.

Analyses of MAPS' completed U.S. study of MDMA-assisted psychotherapy in 20 people with PTSD found an effect size of 1.24 for treatment efficacy, as represented by changes in CAPS score [166]. The estimated effect size for this study may be lower as a result of comparing each active dose with the comparator dose instead of with an inactive placebo, small sample size, and unequal distribution of conditions. The sponsor intends to pool data across studies or perform meta-analyses of CAPS scores across all pilot studies.

The sponsor used Java applications created by Lenth to calculate estimated statistical power for the primary outcome measure of this study. The calculation assumed that active dose 1 and active dose 2 would be equivalent and could be combined, assuming an effect size of 0.8 for the impact of two sessions of MDMA-assisted psychotherapy on symptoms of PTSD [167], reducing the effect size to account for the hypothesized effects of using a comparator dose of 40 mg that is higher than the 25 mg dose employed as an active placebo in a sponsor-supported study. The software calculated an estimated power of 0.33 for a comparison of 18 versus 5, indicating an underpowered study. Had we used the higher effect size of 1.1, power analysis still indicates that this study is underpowered, with an estimated effect size of 0.55, but higher than previously calculated prior to the addition of these subjects. Statistical power estimates were not available for secondary and exploratory measures, as they were previously not used in sponsor-supported studies.

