6.0 Randomization and Blinding

Per Amendment 6, 26 subjects will be enrolled into the study. The randomized portion of the study will be blinded and there will be a 12:9:5 ratio between subjects in the active dose 1, active dose 2, and comparator dose treatment groups. Subjects will be assigned subject numbers, and subjects will be randomized in a blinded fashion.

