9.9.1 Primary Efficacy Analyses

Clinician Administered PTSD Scale-4 (CAPS-4)

The primary efficacy evaluation is the change from baseline to the primary outcome timepoint (visit 12) in the CAPS-4 Global Severity score of PTSD (difference score). The primary efficacy comparison will be made with ANOVA at an alpha level of 0.05. If the primary hypothesis rejects, pairwise comparisons among the treatment groups will be made with t-tests. If the parametric assumptions for the ANOVA and t-test analyses are not met, the analogous nonparametric methods will be used (Kruskall-Wallis, Wilcoxon Rank-Sum).

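### The 125 mg and 100 mg groups are pooled only after an equivalence test with no margin, which at 9 to 12 subjects per dose cannot do its job

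*SAP*

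**What the plan says.** Protocol 12.0 opens the primary analysis with a test between the two active arms: "Active dose 1 and active dose 2 CAPS data at the primary endpoint will be tested for equivalence using confidence intervals". What follows depends on the result. On a pass, "If the two groups are found to be equivalent, then outcomes for the active dose groups will be combined" and compared with 40 mg by a t-test on difference scores at 0.05. On a fail, "If CAPS scores for active dose 1 are not equivalent to active dose 2, then analysis of variance (ANOVA) will be used" across the three groups. The same section repeats the condition for cognition: "Active dose 1 and active dose 2 RBANS and PASAT data will be tested for equivalence using confidence intervals".

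The SAP treats this differently. Its primary analysis (9.9.1) carries no such condition: "The primary efficacy comparison will be made with ANOVA at an alpha level of 0.05", with pairwise t-tests only if the ANOVA rejects. The equivalence test and conditional pooling survive as one bullet in 9.9.3, under exploratory analyses, where the 125 mg and 100 mg "CAPS data at the primary endpoint will be tested for equivalence using confidence intervals". For RBANS and PASAT, SAP 9.9.4 plans a descriptive comparison at the primary endpoint, without an equivalence test.

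Protocol 12.1 gives power for the pooled comparison only, 18 versus 5: "The calculation assumed that active dose 1 and active dose 2 would be equivalent and could be combined". The Protocol allocates 9:9:5. In the SAP, after Amendment 6, "there will be a 12:9:5 ratio between subjects in the active dose 1, active dose 2, and comparator dose treatment groups".

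Neither document states an equivalence margin or the level of the confidence interval.

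**The concern.** An equivalence conclusion is defined by its margin. Without one, two analysts can apply the rule to the same data and reach opposite decisions. Two readings are plausible, and both fail at this sample size.

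- **A true equivalence test**, in which the whole interval must lie inside a margin. The interval is so wide that a margin small enough to mean that the doses act alike will almost always be breached, even when they are identical.
- **A non-significance rule**, in which the interval must include zero. Doses that differ by as much as the effect assumed against 40 mg will usually be merged as equivalent.

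At stake is whether active treatment as a whole is tested against 40 mg in its most powerful form. That is the only comparison for which the Protocol gives power. Under the second reading there is also a risk of a statement about dose that rests on lack of power, in a study meant to inform later trials.

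**Working it through.** Everything is in SD units, because the documents give no CAPS standard deviation. Data are taken as normal with equal variances. Inputs: arm sizes 9:9:5 (Protocol 5.3) and 12:9:5 (SAP 6.0); effects 0.8, 1.1 and 1.24 (Protocol 12.1); two-sided 0.05 (SAP 9.0). The interval level is my assumption; 90% and 95% are both shown.

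**1. The Protocol's own figure.** For a pooled-variance t-test of 18 v 5, SE = √(1/18 + 1/5) = 0.506, df = 21 and critical t = 2.080. At 0.8 the noncentrality is 0.8/0.506 = 1.58 and power is 0.327, matching the stated 0.33. At 1.1 power is 0.546, matching the stated 0.55 (worded there as an effect size, but evidently a power). Both figures assume that pooling is certain.

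**2. Width of the interval for 125 mg minus 100 mg.** Half-width = t × √(1/n₁ + 1/n₂), taken at the true SD.

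| | SE | 90% half-width | 95% half-width |
|---|---|---|---|
| 9 v 9 (df 16) | 0.471 | 1.746 × 0.471 = 0.82 | 2.120 × 0.471 = 1.00 |
| 12 v 9 (df 19) | 0.441 | 1.729 × 0.441 = 0.76 | 2.093 × 0.441 = 0.92 |

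**3. First reading: chance that identical doses pass.** This is the probability that |observed difference| + half-width is less than the margin at a true difference of zero, integrated over the sampling distribution of the SD.

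| Margin (SD) | 9 v 9, 90% CI | 12 v 9, 90% CI | 9 v 9, 95% CI | 12 v 9, 95% CI |
|---|---|---|---|---|
| 0.5 | 0.1% | 0.1% | <0.1% | <0.1% |
| 0.7 | 2.9% | 4.7% | 0.5% | 0.8% |
| 0.8 | 8.7% | 13.5% | 2.0% | 3.3% |
| 1.1 | 45% | 55% | 23% | 33% |
| 1.24 | 62% | 71% | 40% | 52% |
| margin needed for 80% | 1.44 | 1.34 | 1.63 | 1.51 |

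The margins needed for 80% exceed every effect size in Protocol 12.1. For an 80% chance at a margin of 0.8 with a 90% interval, 28 subjects per dose are needed.

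**4. Second reading: the 95% interval includes zero.** This is the probability that the t-test between doses is not significant when they truly differ by 0.8 SD.
- 9 v 9: noncentrality 0.8/0.471 = 1.70, probability 0.642.
- 12 v 9: noncentrality 0.8/0.441 = 1.81, probability 0.594.

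**5. What is lost when the condition fails.** Suppose both doses beat 40 mg by 0.8 SD.
- Three-group ANOVA: λ = 0.8² × n_active × n_40 / N. For 9:9:5, λ = 0.64 × 18 × 5/23 = 2.50, critical F(2,20) = 3.49, power 0.24. For 12:9:5, λ = 0.64 × 21 × 5/26 = 2.58, critical F(2,23) = 3.42, power 0.25.
- Average of the two doses minus 40 mg, using the three-group error term: SE = √[¼(1/n₁ + 1/n₂) + 1/5]. For 9:9:5, SE = 0.506, noncentrality 1.58, df 20, power 0.33. For 12:9:5, SE = 0.499, noncentrality 1.60, df 23, power 0.34.
- At 1.1 SD the ANOVA has 0.42 to 0.44 and the contrast 0.54 to 0.56.

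**6. Passing and then succeeding.** With a margin of 0.8, a 90% interval, identical doses and a true effect of 0.8, the chance of reaching the pooled test and finding p ≤ 0.05 is 4.1% (9:9:5) or 6.1% (12:9:5) by simulation, against the stated 33%. This is not the trial's whole chance of success, because the ANOVA is run when the condition fails.

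**The case against.** The strongest reply is that little hangs on this condition. Several parts of it stand.

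- A reader might infer that the condition can never be met. That is too strong. Identical doses pass about one time in eleven (9 v 9) or one in seven (12 v 9) at a margin of 0.8 with a 90% interval, and about half the time at 1.1. The case is that passing is rare at margins of 0.8 or less, not impossible.
- A reader might infer that active treatment goes untested against 40 mg when the condition fails. The documents do not support this. Protocol 12.0 falls back to the three-group ANOVA, so the loss at 0.8 SD is about 9 points of power, in a study that Protocol 12.1 itself calls underpowered.
- A reader might infer that the SAP's primary result depends on the condition. It does not. SAP 9.9.1 is unconditional, and SAP 9.9 reports effect sizes by treatment group in any case.
- For RBANS and PASAT, the SAP has already dropped the test.
- It is tempting to say that equivalence is judged on endpoint scores while the pooled test uses change scores. The wording may simply name the visit, so this is an ambiguity to clear up, not a demonstrated mismatch.

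None of this makes the condition useful. It has no margin, and at these sizes no margin is both small enough to mean equivalence and wide enough to be met reliably. Nor does the SAP contain an unconditional test of the combined active doses.

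**Conclusion.** The point holds in this limited form: conditional pooling rests on an undefined test that works under neither reading. It matters more in the Protocol, where it selects the primary test and underlies the stated power, than in the SAP, where it affects one exploratory analysis beside an unconditional primary ANOVA.

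The conclusion rests on normal data, equal variances, and a margin expressed in the same SD units as the 0.8 effect. A 95% interval makes passing rarer. Keeping the two replaced subjects in the mITT set changes little: if both fell in one active arm (14 v 9 or 12 v 11), identical doses would pass 16% to 19% of the time at a margin of 0.8 with a 90% interval. The power comparison in step 5 assumes that both doses have the same effect. A misleading equivalence statement is a risk under the second reading, not a certainty, since by-dose results are also reported.

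**What to change.** - **CAPS, both documents.** Remove the equivalence condition from Protocol 12.0 and SAP 9.9.3. Prespecify the contrast of the average of 125 mg and 100 mg versus 40 mg on change in CAPS from baseline to visit 12, reported whatever the difference between doses. In the SAP it stays a supporting analysis beside the primary ANOVA.
- **Dose difference.** Report 125 mg minus 100 mg on CAPS change with its 95% interval, as an estimate, with no claim of equivalence. Naming change scores also removes the ambiguity about which scores are meant.
- **RBANS and PASAT.** Delete the condition in Protocol 12.0, so that it matches the descriptive comparison in SAP 9.9.4.

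The cost is wording in both the Protocol and the SAP, with no new data, visits or subjects. The statistical price is that, if the doses differ, the contrast averages over them; the by-dose estimates beside it make that visible.

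### SAP 9.9.3 leaves two conflicting dissociation regressions in place, and neither adjusts for baseline CAPS, so a dissociation coefficient can partly reflect baseline severity

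*SAP*

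**What the plan says.** SAP 9.9.3 lists, under the CAPS-4 exploratory analyses, two consecutive bullets on dissociation.

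- **The two-regression bullet.** It begins "Two regression analyses will be conducted using (1) all subjects with a Frequency score of 2 or greater", applies the same threshold to intensity, and accepts a positive score "on the CAPS Associated Features 29 or 30 at baseline". A second regression uses baseline DES-II total. These serve as "baseline covariates to determine whether the dissociative subtype of PTSD is predictive of treatment outcomes". The outcome is not named further.
- **The suggestion bullet.** It opens "Here is my suggestion for wording the bullet point above", which is an editor's note and not plan text. It asks whether baseline dissociation variables are "predictive of CAPS Global Severity Score at the Primary Endpoint (dependent variable), a multiple regression analysis will include the following independent variables at baseline": item 29 yes/no, item 30 yes/no, and DES-II total. The list ends "on the CAPS Associated Features 30 or the alternative, and (3) DES-II total score". An empty bullet follows.

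Nothing says which bullet governs. Four other places matter. SAP 2.0 describes the document as an a priori plan, to be final before any analysis. SAP 9.0 counts p of 0.05 or less as significant for all tests. SAP 9.9.1 analyses change from baseline across treatment groups. SAP 8.1 lists Associated Features under the CAPS-4.

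**The concern.** There are two problems, and the first needs no assumption.

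**The analysis is undefined.** An analyst holding this SAP could run two models or one, combine items 29 and 30 or separate them, and choose the outcome under one of the two bullets. Each choice could be defended as planned.

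**The model in the suggestion bullet does not isolate what the analysis is for.** The stated aim is whether dissociation predicts treatment outcome. Regressing the raw endpoint score on dissociation variables alone also picks up the tendency of subjects who start more severe to end more severe. Baseline severity does vary: the protocol sets only a floor of 50 on CAPS (section 4.2.1). Items 29 and 30 are scored within the CAPS, and protocol 5.1.1 allows that dissociation and chronic PTSD may be related. A correlation between the predictors and baseline CAPS is therefore plausible.

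SAP 4.2 says the exploratory objectives are meant to inform future protocol design. A finding that dissociation predicts outcome could shape eligibility or stratification later, although it might reflect baseline severity alone.

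**Working it through.** **Step 1: the two bullets compared.**

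| | Two-regression bullet | Suggestion bullet |
|---|---|---|
| Models | two | one |
| CAPS items 29 and 30 | one either/or criterion | two separate yes/no terms |
| DES-II total | its own regression | third term in the same model |
| Outcome | treatment outcomes, unspecified | endpoint CAPS Global Severity |
| Baseline CAPS named | no | no |
| Dose group named | no | no |

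**Step 2: the plan's own figure.** The documents give no operating characteristic for this regression, so there is nothing to reproduce. The simulation below borrows the effect size of 0.8 from protocol 12.1 as its dose effect. That section's power of 0.33 for 18 versus 5 does reproduce. The noncentrality is 0.8 × √(18 × 5 / 23) = 1.58 on 21 df, and a two-sided t-test at 0.05 gives 0.327. This does not bear on the dissociation model.

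**Step 3: what the unadjusted slope estimates.** Let r be the correlation of dissociation with baseline CAPS, and rho the correlation of baseline with endpoint CAPS. Suppose dissociation has no effect beyond baseline severity. In SD units, with DES-II as sole predictor:

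- Raw endpoint: slope = r × rho. At r = rho = 0.5 this is 0.25 (simulated 0.251).
- Change score without baseline CAPS: slope = r × rho − r = −0.25 (simulated −0.249). Borrowing the difference score from the primary analysis only reverses the sign.
- Endpoint adjusted for baseline CAPS and dose: slope = 0 (simulated 0.004).

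**Step 4: rejection rates.** Inputs from the documents: n = 26 split 12:9:5 (SAP 6.0) and two-sided 0.05 (SAP 9.0). Assumptions: r, rho, 30% prevalence for each item, and the correlation among the three predictors left after baseline CAPS is accounted for. In the table, the upper end takes that residual correlation as zero and the lower end as 0.4. There were 4,000 to 6,000 simulated trials per setting. Two standard errors are about 0.9 points near 9% (2 × √(0.09 × 0.91 / 4,000)) and 1.3 points near 21%.

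Suggestion-bullet model, rho = 0.5, no dissociation effect beyond baseline severity:

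| r | DES-II term | Joint test of three terms |
|---|---|---|
| 0 | about 5% | about 5% |
| 0.3 | 7–9% | 8–11% |
| 0.5 | 11–15% | 16–21% |

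Varying rho from 0.3 to 0.7, with residual correlation 0.4, moves the joint test over 4.8–4.9% at r = 0, 5.4–7.6% at r = 0.2, 6.6–12.7% at r = 0.3 and 8.9–29.6% at r = 0.5.

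**Step 5: which omission matters.** Joint test at r = rho = 0.5, residual correlation 0.4:

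- As written: 16.6%.
- Adding dose only: 16.5%.
- Adding baseline CAPS only: 5.6%.
- Adding both: 5.6%.
- Change score without baseline CAPS: 16.7%.

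Baseline CAPS does the work.

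**Step 6: the two-regression bullet, read without covariates.** For r from 0.3 to 0.5 at rho = 0.5, the either/or indicator rejects in 9–17% of trials and DES-II alone in 11–21%. Retaining this bullet instead does not cure the problem.

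**The case against.** **The rates are errors only for one question.** The suggestion bullet asks whether baseline dissociation variables predict endpoint CAPS. If they correlate with baseline CAPS, they do predict it marginally, and rejecting is then the right answer. This stands. The rates above are false positives only for prediction beyond baseline severity. The aim in the two-regression bullet makes that the more useful question, but the SAP does not state it. Adjusting changes the quantity estimated, and the plan should say so.

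**The correlations are assumed.** This stands too. The protocol says only that a relationship may exist. At r = 0 there is no inflation, and at 0.2 it is slight.

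**The stakes are low.** The analysis is exploratory, in a pilot meant to estimate effect sizes, and no decision in the documents rests on it. That limits the grade. It does not excuse leaving the model undefined.

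Three stronger readings are tempting, and the documents do not support them:

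- A reader might infer that omitting dose also lets baseline severity pass as dissociation. Dose is randomised, so its omission adds residual noise and chance imbalance, not this confounding. Step 5 shows that adding dose alone changes nothing.
- A reader might infer that only the suggestion bullet is deficient. The other bullet names neither covariate either.
- A reader might infer from the comment that the plan was altered after results were seen. A stray editing note says nothing about timing.

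**Conclusion.** The point holds, as a correction that should be made to an exploratory analysis. That SAP 9.9.3 carries an unresolved drafting comment and two incompatible specifications is plain from the text.

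The statistical part is conditional. It needs dissociation to correlate with baseline CAPS and baseline CAPS to correlate with endpoint CAPS, and the documents quantify neither. With 26 subjects and rho of 0.5, the excess over the nominal 5% runs from nothing at r = 0 to about 6–10 points for DES-II and 11–16 points for the joint test at r = 0.5. It depends on the assumed correlation among predictors. The direction is robust; the exact percentages are not. Adjustment for baseline CAPS and dose returns the rate to about 5% throughout. The primary CAPS comparison is untouched.

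**What to change.** Delete the drafting comment, the empty bullet and both dissociation bullets. Replace them with one specification:

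- **Question:** does baseline dissociation predict visit 12 CAPS Global Severity beyond baseline severity?
- **Main exploratory model:** visit 12 CAPS Global Severity on baseline CAPS Global Severity, randomised dose group, and one indicator that is positive when item 29 or item 30 meets the frequency and intensity thresholds already in the SAP.
- **Named supportive analysis:** the same model with baseline DES-II total in place of the indicator.
- **Reporting:** estimates with confidence intervals, labelled exploratory and without multiplicity control.

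One model must be named as main. Each holds about 5% alone, but testing both at 0.05 gives at least one false positive in about 9–11% of null trials.

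The cost is SAP wording and three model degrees of freedom: one for baseline CAPS and two for dose group. With 26 subjects, 26 − (1 + 1 + 2 + 1) = 21 residual df remain. All the data are already collected.
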